### **Analysis of Secondary Outcomes**

Descriptive statistics will be presented for all secondary outcomes by trial arm at the time points collected and presented graphically where appropriate.

#### *Depression Severity and Symptomatology at 12 months*

The estimate of the effect of the intervention on PHQ-9 scores at 12 months will be extracted from the primary analysis model and presented with 95% confidence intervals and associated p-value.

#### *Binary Depression Severity*

A logistic mixed effects model will be used to compare PHQ-9 depression caseness (scores  $\geq 10$ ) between treatment arms. The model specification and checking will be similar to the primary analysis, but using depression caseness as the outcome. Any covariates identified for the primary outcome will be included in the model. Odds ratios and 95% confidence intervals will be presented for the effect of the intervention at 4 and 12 months.

#### *Quality of Life*

The primary analysis will be repeated for the continuous scores of the SF-12 physical and mental component scores, adjusting for baseline values of the outcome in question and any relevant covariates identified for the primary outcome. Estimates of the effect of the intervention will be derived at 4 and 12 months.

Frequencies of responses for each EQ-5D dimension (mobility, self-care, usual activities, pain, anxiety/depression) will be presented descriptively by trial arm. EQ-5D data will be formally analysed as part of the economic evaluation.

#### *Psychological Anxiety*

The primary analysis will be repeated for the continuous total score of the GAD-7, adjusting for baseline values of the questionnaire and any relevant covariates identified for the primary outcome. Estimates of the effect of the intervention will be derived at 4 and 12 months.

#### *Mental Health Medication*

A logistic mixed effects model will be used to compare whether any mental health medication was prescribed. The model specification and checking will be similar to the primary analysis, but using any self-reported medication (yes or no) as the outcome. Any relevant covariates identified for the primary outcome will be included in the model. Odds ratios and 95% confidence intervals will be presented for the effect of the intervention at 4 and 12 months.

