#### Sample Size

To detect a minimum standard effect size of 0.3 with 80% power and a two-sided 5% significance level would require 352 patients (176 in each group). Although this is an individually-randomised trial, there may be potential clustering at the level of each collaborative care case manager and hence the sample size was inflated to account for this. Based upon an ICC = 0.02 and a caseload size of 20, the design effect would be 1.38 ( $1 + (20 - 1) \times 0.02$ ) and 486 patients (243 in each group) would be required.

The original trial sample size allowed for 10% loss to follow-up, resulting in a total of 540 patients (270 in each group). Following the inspection of interim recruitment figures and disproportionate dropout from the collaborative care arm, this assumption was revised (Substantial Amendment 17). Allowing for a loss to follow-up of 26%, the final sample size needed is 658 patients (329 in each group).

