## Data Collection Schedule

Table 1: Data Collection Schedule

	Invitation	Baseline	Diagnostic Interview	4 month follow-up	12 month follow-up
Consent/Decline	•				
Demographic questionnaire	•				
Whooley questionnaire	•	•			
Physical health problems	•				
Falls questions	•				
PHQ-9		• 	• 	•	•
SF-12		•		•	•
EQ-5D		•		•	•
GAD-7		•		•	•
PHQ-15		•		•	•
CD-RISC 2		•		•	•
Medication questionnaire		•		•	•
M.I.N.I.			•		
Economic evaluation		•		•	•
Objective medication data		•		•	•

 PHQ-9 at baseline will be reported in the participant baseline characteristics

 PHQ-9 at diagnostic interview will be used as covariate in the analyses

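### The mental health medication model does not name baseline medication use as a covariate, although it is collected and the SF-12 and GAD-7 models adjust for their own baselines

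*SAP*

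**What the plan says.** The Mental Health Medication paragraph in section 6 of the SAP plans a logistic mixed model, "using any self-reported medication (yes or no) as the outcome". Its specification is to resemble that of the primary analysis, with the addition of relevant covariates identified for the primary outcome. The primary model's named baseline covariates are the diagnostic-interview PHQ-9 and the SF-12 physical component score. Baseline medication use is not named.

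The neighbouring outcomes are treated differently. Under Quality of Life, the SF-12 component scores are analysed "adjusting for baseline values of the outcome in question". Under Psychological Anxiety, the GAD-7 is adjusted for its own baseline in the same way.

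Baseline medication data should exist. Table 1 marks the medication questionnaire at baseline, 4 months and 12 months. Item 2 of the Secondary Analyses lists mental health medication use among candidate baseline predictors of PHQ-9. The outcome description in section 4 mentions only the follow-up questionnaires, but it does not say that the baseline was skipped.

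**The concern.** A patient's antidepressant use before randomisation is likely to be the strongest single predictor of use 4 or 12 months later. The SAP has this variable but leaves its inclusion to a test of something else: whether it predicts the 4-month PHQ-9 at p<0.10, after control for PHQ-9 at randomisation, and then remains in a combined regression. A variable could dominate later medication use and fail that screen. Whether the medication model contains its own baseline is therefore decided by the data, on an unrelated criterion.

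What is at stake is power to detect an effect on a secondary outcome, and consistency across the secondary models. Randomisation was simple and unstratified, so the design did not balance baseline use between arms. The patient-level correlation in the mixed model does not replace baseline adjustment, because it links the two follow-up measurements to each other and not to the pre-randomisation value.

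**Working it through.** **Number of patients.** For a standardised effect of 0.3 with "80% power and a two-sided 5% significance level", the t-based calculation gives 175.4 per arm, rounded up to 176 (352 in total). With the stated design effect, 1 + 19 × 0.02 = 1.38, and 352 × 1.38 = 485.8, so "486 patients (243 in each group) would be required". Then 486/0.74 = 656.8, which is 658 with rounding and equal arms. The plan's figures reproduce. They assume no covariate adjustment, so this point does not alter them. I use 243 analysed per arm below.

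**Assumed inputs (none is in the SAP).** Baseline use 12%; later use reported by 85% of baseline users and 4% of non-users under usual care; conditional log-odds effect -0.9. The calculation is for one time point, without the other covariates, the random effect or clustering.

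**Risks.**
- Usual care: 0.12 × 0.85 + 0.88 × 0.04 = 0.1372.
- Collaborative care: multiplying the odds by exp(-0.9) = 0.407 takes 0.85 to 0.697 and 0.04 to 0.0167. The overall risk is 0.12 × 0.697 + 0.88 × 0.0167 = 0.0983.

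**Without baseline use.**
- Log odds ratio: logit(0.0983) - logit(0.1372) = -0.38.
- SE = √[1/(243 × 0.1372 × 0.8628) + 1/(243 × 0.0983 × 0.9017)] = √(0.0348 + 0.0464) = 0.285.
- z = 0.377/0.285 = 1.32, so power is Φ(1.32 - 1.96), about 26%.

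**With baseline use.** The information in each stratum is 1/[1/(n p₀q₀) + 1/(n p₁q₁)], with n patients per arm, p₀ and p₁ the usual-care and collaborative-care risks, and q = 1 - p.
- Users (n = 29.2): 1/(1/3.72 + 1/6.16) = 2.32.
- Non-users (n = 213.8): 1/(1/8.21 + 1/3.50) = 2.46.
- SE = 1/√(2.32 + 2.46) = 0.46.
- z = 0.9/0.46 = 1.97, so power is about 50%.

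Simulation of the same scenario agrees: power rises from about 26% to 52%, the median SE of the log odds ratio rises from 0.29 to 0.47, and the estimated effect moves from about -0.38 to -0.92.

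**Sensitivity to the assumptions.** A second set of simulations used 486 analysed patients, a conditional odds ratio of 0.4, baseline use of 10-30%, continuation of 70-90% and new use of 3-5%. Power rose from 0.17-0.66 unadjusted to 0.36-0.86 adjusted, a gain of 16 to 37 points depending on the scenario.

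**Variance on the risk-difference scale**, for context only, since the SAP reports odds ratios. The residual share is [b·s(1-s) + (1-b)·q(1-q)] / [p(1-p)], where b is baseline use, s later use among users, q later use among non-users, and p = b·s + (1-b)·q.
- At b = 10%, s = 80%, q = 5%: 0.05875/0.10938 = 0.54, a cut of 46%.
- At b = 15%, s = 85%, q = 3%: 0.04386/0.12959 = 0.34, a cut of 66%.

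These are the extremes over 10-15% use, 80-85% continuation and 3-5% new use.

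**The case against.** **The gap may be one of wording.** The medication model is to resemble the primary one, and the primary model adjusts for a pre-randomisation level of its own outcome. A sympathetic analyst might carry that over. This stands as a reason to call the point under-specification rather than a decision to exclude. It does not close the gap: the SF-12 and GAD-7 paragraphs state the adjustment, the medication paragraph does not, and Table 2 offers no reason.

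**The unadjusted comparison is valid.** A reader might infer that chance imbalance in baseline use biases the result. Under randomisation it does not; the loss is one of efficiency. A reader might also expect adjustment to narrow the confidence interval. On the log odds ratio scale it does the opposite here. The benefit is a larger conditional effect relative to its SE.

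**The size is assumed.** Prevalence, persistence and effect size all come from outside the SAP, so the power figures are illustrative. The direction is the same in every scenario examined.

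**Does the same criticism reach PHQ-9?** A reader might infer so, because Table 1's first footnote says "PHQ-9 at baseline will be reported in the participant baseline characteristics" and the models use only the interview score. The SAP does not support that reading as a fault. The interview score is itself pre-randomisation, and the two footnotes allocate the roles by stated choice. If both scores correlate 0.5 with the outcome and 0.7 with each other (assumed), R² rises from 0.25 to 2 × 0.25 × (1 - 0.7)/(1 - 0.49) = 0.294, and residual variance falls by 1 - 0.706/0.75 = 6%. Over correlations of 0.4-0.6 with the outcome and 0.5-0.7 with each other, the reduction is 3-19%. A second score would also run into the complete-covariate requirement in Analysis Population and the ban on imputation in Principles. Leaving it out is a reasonable trade-off.

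**Conclusion.** The point holds for the medication model only. The SAP collects baseline medication use, adjusts two other secondary outcomes for their own baseline, and leaves this one to a screen against PHQ-9. Naming the covariate would raise power, illustratively from about 26% to 52% under the assumptions above, with a gain of 16 to 37 points over the wider set. It would not reduce the SE of the log odds ratio.

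Severity is minor and the change is a nearly free improvement. Medication is one of several secondary outcomes, Table 2 describes the secondary analyses as more exploratory, and neither the primary conclusion nor the sample size changes.

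**What to change.** In the Mental Health Medication paragraph of section 6, state that the model adjusts for baseline mental health medication use (yes/no) as a fixed covariate, whatever the result of the predictor screen in item 2 of the Secondary Analyses.

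State how missing baseline values are handled, for example with a separate missing category. That keeps every patient under the complete-covariate rule and stays within the no-imputation rule. It would also help to mention the baseline questionnaire in the medication description in section 4, so that it agrees with Table 1.

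The cost is a sentence or two of SAP text, one extra covariate (with a missing level if needed), and an odds ratio to be read as conditional on baseline use. No new data are needed.

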#### *Mortality*

The number of deaths occurring during the 12 months trial period will be summarised by trial arm and overall. A chi-square test will be used to compare proportions between trial arms if more than five participants died in each arm.

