### **Secondary Outcomes**

- Depression severity and symptomatology at 12 months (PHQ-9)
- Binary Depression Severity at 4 & 12 months (PHQ-9), using scores  $\geq 10$  to designate moderate depression caseness
- Quality of Life at 4 & 12 months (SF-12 and EQ-5D)
- Psychological Anxiety at 4 & 12 months (GAD-7)
- Mental Health Medication at 4 & 12 months
- Mortality at 4 & 12 months

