#### *Mortality*

Mortality was established by flagging all randomised participants to the NHS Information Centre at regular intervals. Members of the research team recorded any identified deaths on the study management database.

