## **6. Analysis**

### **Principles**

All analyses will be conducted on intention to treat basis (ITT), including all randomised participants in the groups to which they were allocated. Any post randomisation exclusions will be referred to the independent statistician on the DMEC for approval. Analyses will be conducted in Stata version 13 or later, using 2-sided significance tests at the 5% significance level. Results will be presented with 95% confidence intervals where appropriate. The statistician conducting the analyses will remain blind to treatment group until the primary analysis is finalised and checked by the second statistician.

Any missing data will be reported for all predictor and outcome variables by trial arm and response rates compared. No imputations will be undertaken, and the impact of missing data will be explored as part of secondary analyses of the primary outcome.

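### The only mortality test is withheld unless more than five die in each arm, with no fallback test or effect estimate, and 4-month mortality has at most a descriptive summary

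*SAP*

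**What the plan says.** Section 4 of the SAP (Secondary Outcomes) lists "Mortality at 4 & 12 months". Ascertainment covers everyone randomised: "Mortality was established by flagging all randomised participants to the NHS Information Centre at regular intervals".

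The analysis is two sentences under Mortality in section 6. The first is "The number of deaths occurring during the 12 months trial period will be summarised by trial arm and overall". The second is "A chi-square test will be used to compare proportions between trial arms if more than five participants died in each arm". The paragraph does not say what is done when the condition fails, and it names no effect measure or interval.

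The sentence that opens Analysis of Secondary Outcomes adds: "Descriptive statistics will be presented for all secondary outcomes by trial arm at the time points collected". The Principles section sets "using 2-sided significance tests at the 5% significance level" and promises 95% confidence intervals where they are appropriate. The paragraphs on caseness, SF-12, GAD-7 and medication each ask for an effect estimate at both follow-ups; the mortality paragraph does not. Table 2 (Departures from the Protocol) has no mortality entry. The SAP states no expected death rate.

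**The concern.** There are two problems.

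First, the gate is on the wrong quantity. The usual caution about the chi-square approximation concerns expected counts under the null hypothesis, which depend on the total number of deaths and the allocation ratio. The SAP uses the observed count in each arm, and that count depends partly on the difference being tested. For a given total, moving deaths from one arm to the other closes the gate once the smaller arm falls to five. Because nothing replaces the test, a clear imbalance could be reported with no planned inference, and any test added later would be post hoc.

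Second, the outcome is listed at two time points, but the mortality paragraph gives a summary and a test for the 12-month period only.

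**Working it through.** **1. Denominator.** The SAP's Sample Size section gives: "Based upon an ICC = 0.02 and a caseload size of 20, the design effect would be 1.38". Then 352 × (1 + 19 × 0.02) = 352 × 1.38 = 485.8, so 486, or 243 per arm. With 26% loss, 243 / 0.74 = 328.4, so 329 per arm and 658 in total. The plan's figure is reproduced. I use 329 per arm below. Simple randomisation will not give exactly equal arms, but the effect on these results is small.

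**2. When chi-square is valid.** Expected deaths per arm = total deaths × 329/658 = total/2. This reaches 5 at 10 deaths. Expected survivors per arm are 329 − total/2, which is never the limiting cell.

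**3. Fixed total of 24 deaths (illustrative; expected 12 per arm in every row).** Two-sided tests, chi-square without continuity correction.

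| Split | SAP rule | Chi-square p | Fisher p |
|---|---|---|---|
| 12 v 12 | tested | 1.00 | 1.00 |
| 8 v 16 | tested | 0.096 | 0.144 |
| 6 v 18 | tested | 0.013 | 0.020 |
| 5 v 19 | not tested | 0.0036 | 0.0057 |
| 3 v 21 | not tested | 0.0002 | 0.0002 |

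The expected counts are the same throughout, so validity does not explain why testing stops at 5 v 19.

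**4. Other tables.**
- Not tested: 0 v 10 (expected 5.0 per arm, Fisher p=0.0018), 3 v 15 (expected 9.0, p=0.0068), 5 v 20 (expected 12.5, p=0.0034).
- Tested: 6 v 6 (p=1.00).
- Low balanced counts such as 4 v 4 are also not tested.
- With 0, 1, 2, 3, 4 or 5 deaths in one arm, Fisher p<0.05 needs 6, 8, 10, 12, 13 or 15 in the other. The rule tests none of these.

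**5. How often it matters.** Let X₁ ~ Bin(329, p₁) and X₂ ~ Bin(329, p₂), independent.
- P(tested) = P(X₁ ≥ 6) × P(X₂ ≥ 6).
- P(significant) = the sum over all (x₁, x₂) of P(x₁)P(x₂) for which the test is done and p<0.05.

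The rule uses chi-square. *Expected-count choice* means chi-square if total/2 ≥ 5, otherwise Fisher. All death rates are assumptions.

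| 12-month mortality | Tested under rule | Significant: SAP rule | Significant: Fisher always | Significant: expected-count choice |
|---|---|---|---|---|
| 1% v 4% | 11.4% | 2.9% | 63.5% | 73.0% |
| 1.5% v 4.5% | 37.2% | 12.7% | 55.4% | 63.9% |
| 2% v 6% | 64.5% | 42.5% | 70.8% | 76.8% |
| 3% v 6% | 93.1% | 39.9% | 39.3% | 46.5% |
| 4% v 8% | 99.1% | 57.7% | 51.9% | 58.6% |

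With equal rates, a test is done in 42% of trials at 2% and in 98% at 4%. The expected-count choice rejects in 4.7% and 5.0% of those trials, so it holds the 5% level there.

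**6. Time points.** The outcome list names 4 and 12 months. The mortality paragraph covers the 12-month period. The only text that reaches 4 months is the general descriptive sentence for all secondary outcomes, which supplies no estimate or test.

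**The case against.** The strongest reply is that nothing is concealed. Deaths are summarised by arm whatever their number. They appear again among the dropout categories under Trial Progression, and again as serious adverse events reported by arm. Anyone shown 0 v 10 can compute Fisher's test. Mortality is one of several secondary outcomes, Table 2 describes secondary analyses as more exploratory, and the trial was sized on the PHQ-9: "To detect a minimum standard effect size of 0.3 with 80% power and a two-sided 5% significance level". The rule is mainly a low-count gate, and at higher death rates it almost never closes.

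Most of that stands, and it rules out four stronger readings that a reader might infer.

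- *The rule hides a mortality difference or biases reporting towards no difference.* Not supported: counts by arm are always given. A planned p-value is withheld, and the paragraph names no interval, although the general promise of intervals in Principles might be read to cover one.
- *Balanced deaths are tested and unbalanced ones are not.* Not supported in general: at 2% in both arms, 58% of trials go untested, and 6 v 18 is tested. The dependence on imbalance arises, for a given total, once the smaller arm has five or fewer deaths.
- *Four-month mortality is never analysed.* Too strong: the general descriptive sentence can be read to cover a 4-month count by arm.
- *The rule loses power whatever the death rate.* Not supported: from about 3% in the lower arm it does as well as always using Fisher's test, and at 4% v 8% slightly better (58% v 52%).

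What the reply does not answer is that the condition rests on the wrong counts, that nothing is specified when it fails, and that the two statements of the time points do not match.

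**Conclusion.** The point holds as a defect of specification in a secondary outcome. Followed as written, the rule withholds valid tests in tables with clear imbalance and puts nothing in their place.

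Its cost depends on a death rate that the SAP does not give. Against Fisher's test always done, significant results fall from 64% to 3% at 1% v 4%, from 55% to 13% at 1.5% v 4.5%, and from 71% to 43% at 2% v 6%. There is no loss against Fisher at 3% v 6% or 4% v 8%. Against the expected-count choice, the loss there is about 7 and 1 percentage points. The document does not show which range applies. These figures assume 329 per arm and independent binomial deaths.

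The 4-month gap is a smaller, separate inconsistency: the time point is listed, but no estimate or comparison is specified for it. The primary analysis is unaffected by either part.

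**What to change.** Replace the conditional sentence with wording such as:

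> Deaths by 12 months will be compared between arms in all randomised participants, whatever the observed counts, by a chi-square test if all expected counts are at least 5 and by Fisher's exact test otherwise. The risk difference will be given with a score or exact 95% confidence interval. Deaths by 4 months will be reported by arm with the same estimate and interval where dates of death allow.

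Choosing on expected counts is preferable to Fisher's test throughout, which gives up some power at higher death rates.

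The cost is a few lines of text and a short extra analysis. Fisher's test is slightly conservative at low counts. The 4-month figure needs dates of death. The SAP says that deaths and status changes are recorded but does not say that dates are held, so this should be confirmed first. If they are not held, the outcome list should be brought into line with what can be reported.

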### **Analysis of Other Collected Data**

Descriptive statistics will be presented for physical symptom severity (PHQ-15) and psychological resilience (CD-RISC 2) by trial arm at the time points collected.

### **Sub-group Analyses**

No sub-group analyses will be conducted as part of this analysis.

### **Adverse Events**

Frequencies of any reported adverse events will be summarised by trial arm and overall. Figures will include a breakdown by type of event and relatedness to the intervention. The details of adverse events will be categorised and reported descriptively. The number and percent of patients experiencing at least one adverse event as well as the average number of adverse events per patient will be presented.

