### 3. Trial Design

#### Summary

The CASPER trial is a 2-arm, unblinded, pragmatic randomised controlled trial with randomisation at the patient level. The two arms are:

(1) Collaborative Care with Behavioural Activation (CC)

- Customised low intensity care programme delivered to an established protocol by a case manager (mental health / IAPT worker)
- 8-10 weekly sessions, first session conducted face to face, subsequent sessions fact to face or by telephone according to patient preference
- Elements of CC: telephone support, symptom monitoring and active surveillance, low intensity psycho-social management / behavioural activation

(2) Usual Primary Care (UC)

- GP delivered usual care management of sub-threshold depression in line with NICE guidance

Full details of the background and design of the trial are given in the study protocol (latest version at time of writing: Version 2.8, 3 Dec 2013).

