### *Adverse Events*

Serious Adverse Events (SAEs), i.e. any deaths, unscheduled hospitalisations and any other medically important conditions were identified on an ongoing basis and documented on an SAE form. Outcome status and relatedness to the intervention (as assessed by a member of the trial management group) were recorded.

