#### *Economic Evaluation*

Economic questionnaire items covered participants' health resource use, such as hospital visits and stays as well as use of further NHS and other health support services.

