## 5. Data

### Data Sources

- Case Report Forms (CRFs)
  - Decline Form
  - Background Information Form
  - Baseline Questionnaire
  - Four Month Follow-up Questionnaire
  - Twelve Month Follow-up Questionnaire
  
- Study Management Database
  - Number of Invites Sent
  - Consent and Randomisation Dates
  - Centre, Practice and GP Codes
  - Randomised Allocation Group
  - Case Manager Allocations
  - Questionnaire Return Dates
  - Status Changes (death, dropout from treatment, follow-up or trial)
  - M.I.N.I. Diagnostic Interview Responses and Outcome
  - PHQ-9 at Diagnostic Interview
  - Web Completed Questionnaire Data (baseline, four months, twelve months)
  
- Patient Case Management Information System (PC-MIS)
  - Collaborative Care Session Dates
  - Collaborative Care Completion Status
  - Collaborative Care Session Type (Phone or Face-to-face)
  
- Local Investigator Spreadsheets
  - Adverse Event Details

All data will be available in csv format before being imported to the statistical analysis software.

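### Non-fatal serious adverse events may not be found equally in the two arms, and the SAP tabulates them by arm with no caveat and no cross-check

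*SAP*

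**What the plan says.** Under Other Collected Data, the SAP's Adverse Events section explains that SAEs, meaning "any deaths, unscheduled hospitalisations and any other medically important conditions were identified on an ongoing basis and documented on an SAE form", also had outcome and relatedness recorded. It gives no schedule or route of discovery for either arm. Data Sources places adverse event details in "Local Investigator Spreadsheets", separate from the case report forms and questionnaires.

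The Trial Design summary calls the trial unblinded. It describes collaborative care as "8-10 weekly sessions, first session conducted face to face", with elements that include "telephone support, symptom monitoring and active surveillance". Usual care is management by the GP. The scheduled trial contact that both arms share after randomisation is the postal questionnaire at 4 and 12 months (Follow-up).

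The Adverse Events section of the Analysis chapter plans frequencies by arm and overall, and a breakdown by type and relatedness. It adds that "The number and percent of patients experiencing at least one adverse event as well as the average number of adverse events per patient will be" shown. It plans no test and says nothing about how events were ascertained.

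Two other sources work the same way in both arms. Deaths are established by NHS flagging of all randomised participants (Mortality, under Secondary Outcomes) and are summarised by arm as an outcome of their own. The economic questionnaire covers resource use "such as hospital visits and stays as well as use of further NHS and other health support services", and Table 1 schedules it at baseline, 4 and 12 months. Its analysis lies outside this SAP (Scope).

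**The concern.** A case manager who speaks to a participant every week has many chances to hear of a hospital admission. A usual care participant has no comparable scheduled contact with the trial. If such contacts feed the SAE forms, the same event is more likely to be recorded in collaborative care than in usual care.

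A by-arm table built only on those forms could then show an excess that reflects contact, or hide a real reduction. The percent with an event and the mean events per patient are the figures that readers will compare as the safety result, whether or not a test is attached. The population is over 65, and unscheduled hospitalisation is one of the SAE types. The SAP nevertheless neither qualifies the table nor sets it against the hospital data that both arms supply on the same form.

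**Working it through.** **The plan's own figures.** The SAP states no adverse event rate, so there is none to reproduce. The only design figure needed is the arm size. 352 x 1.38 = 485.8, so 486 patients or 243 per arm. 243 / (1 - 0.26) = 328.4, so 329 per arm and 658 in total, which agrees with the Sample Size section.

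**Inputs from the SAP.** 329 per arm; 8-10 weekly sessions; an adverse event window of 12 months, taken as 52 weeks.

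**Inputs that are assumptions.** Equal true risk of a non-fatal SAE in both arms; events spread evenly over the year; at most one event per patient; all collaborative care participants attend the sessions; detection of 0.90 in collaborative care while the difference lasts, against 0.80, 0.70 or 0.60 in usual care.

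**Formulas.** Let d1 be detection in collaborative care, d0 detection in usual care, and w the number of weeks of extra contact.

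- Difference lasts all 12 months: apparent risk ratio = d1 / d0.
- Difference lasts only w weeks, with detection equal to d0 in both arms otherwise: apparent risk ratio = 1 + (w / 52) x (d1 / d0 - 1).

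The true risk cancels, so neither ratio depends on it.

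| Assumed detection (d1 vs d0) | 8 weeks only | 10 weeks only | All 12 months |
|---|---|---|---|
| 0.90 vs 0.80 | 1.019 | 1.024 | 1.125 |
| 0.90 vs 0.70 | 1.044 | 1.055 | 1.286 |
| 0.90 vs 0.60 | 1.077 | 1.096 | 1.500 |

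Example for one cell: 1 + (10 / 52) x (0.90 / 0.60 - 1) = 1 + 0.1923 x 0.5 = 1.096.

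**In patients, at an assumed true risk of 15%.**

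- Usual care at 0.60 detection: 329 x 0.15 x 0.60 = 29.6.
- Collaborative care at 0.90 for the whole year: 329 x 0.15 x 0.90 = 44.4. The observed risks are 0.135 and 0.090. The standard error of the difference is the square root of (0.135 x 0.865 + 0.090 x 0.910) / 329, which is 0.0246, so z = 0.045 / 0.0246 = 1.83.
- Collaborative care at 0.90 for the contact weeks only: 29.6 x 1.077 to 29.6 x 1.096, about 32.

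The same detection rates thus give about 44 versus 30 patients or about 32 versus 30, depending only on how long the extra detection lasts. The SAP does not say which is closer.

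**The case against.** The strongest reply is that the SAP never says case managers report SAEs, nor how usual care events are found. The reporting route is usually left to the protocol, which is not shown here and may set a common one. That stands, and it limits the point. A reader might infer that the SAE comparison is confounded with surveillance by design; the text supports only that it is open to differential ascertainment.

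Second, the planned presentation is descriptive. No test or estimate is biased, and the SAP does not call the table its safety comparison. That stands too. It does not remove the case for a caveat, because by-arm percentages and means invite comparison.

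Third, a ratio of 1.5 needs the detection gap to persist for 12 months, while the sessions cover 8-10 of 52 weeks. Some participants will receive no sessions, and the Sample Size section reports disproportionate dropout from collaborative care, which could lower detection in that arm. This is right: 1.5 is the top of an assumed range, not an expected value.

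Fourth, questionnaire hospital stays are symmetric only in method. They depend on return, which may differ by arm, and the SAP does not say that planned and unscheduled stays are separated. This rules out replacing the SAE table with them. It does not rule out showing them alongside. That the economic analysis is detailed elsewhere is no bar: the SAP already tabulates EQ-5D dimensions descriptively while leaving their formal analysis to the economic evaluation.

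**Conclusion.** The point holds for non-fatal SAEs, as a weakness of presentation. The by-arm figures could differ because of unequal contact alone, and the SAP provides neither a caveat nor a cross-check. Deaths are outside the point, because central flagging treats both arms alike.

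The apparent risk ratio with no true difference is about 1.02-1.10 if extra detection ends with the sessions, and about 1.12-1.50 if it lasts the year. Both ranges rest on assumed detection of 90% versus 60-80% and on equal true risk. The documents fix neither the size nor the presence of a difference.

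A reader might conclude that the safety table cannot be interpreted, or that an excess in collaborative care should be expected. The SAP does not support either reading: it does not describe the reporting route by arm, and the distortion may be small. What is justified is a low-cost improvement.

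**What to change.** In the Adverse Events section of the Analysis chapter:

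- Keep the planned SAE table.
- Beside it, present by arm the number and percent of participants with at least one hospital stay, and the number of stays, from the 4- and 12-month questionnaire items. Give response rates by arm, and show the NHS-flagged deaths with them.
- State that non-fatal events from SAE forms may not be ascertained equally between arms, and base the between-arm reading of hospitalisation on both sources.
- If a time split is wanted and event dates allow it, use the same fixed periods since randomisation in both arms, for example 0-4 and 4-12 months. A split into during and after the sessions has no counterpart in usual care.

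The cost is a few sentences and one or two descriptive tables from data already collected; no new model is needed. The downside is that questionnaire stays are missing for non-responders, possibly to a different extent in each arm, and may include planned admissions. The response rates and a footnote should make this visible.
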